4.3. Women of Childbearing Potential

A woman of childbearing potential (WOCBP) is considered fertile following menarche and until becoming post-menopausal unless permanently sterile (Section 4.3.1). If fertility is unclear and a menstrual cycle cannot be confirmed before the first study drug dose (W1D1), subject should be considered of childbearing potential and applicable pregnancy tests completed.

A WOCBP must have a negative serum or urine pregnancy test (minimum sensitivity 25 IU/L or equivalent units of human chorionic gonadotropin) within 24 hours before the start of study treatment. An extension up to 72 hours before the start of study treatment is permissible in situations where results cannot be obtained within the standard 24-hour window.

4.3.1. Women of Non-Childbearing Potential

Female subjects must meet 1 of the following criteria to be considered of non-childbearing potential:

- Have undergone hysterectomy or bilateral salpingectomy/oophorectomy or bilateral tubal occlusion/ligation at least 1 month before Informed Consent.
- Are medically confirmed to be post-menopausal (cessation of regular menses for at least 12 consecutive months before W1D1 with no alternative pathological or physiological cause).

Females with less than 12 months of amenorrhea must have a serum follicle stimulating hormone (FSH) level > 40 mIU/mL on 2 measurements performed 2 months apart

If fertility is unclear and a menstrual cycle cannot be confirmed before the first dose of study treatment (W1D1), subject should be considered of childbearing potential and applicable pregnancy tests completed.

4.3.2. Acceptable Methods of Contraception

Heterosexually active female subjects of childbearing potential must agree to use at least 2 forms of highly effective methods of contraception, including at least 1 barrier method for the duration of the study and at least 120 days after the last dose of study drug. Women should not donate eggs during this posttreatment period.

Highly effective methods of contraception are those that, alone or in combination, result in a failure rate of $< 1\%$ per year when used consistently and correctly (i.e., perfect use) and include:

- Combined (estrogen and progestogen containing) hormonal contraception associated with inhibition of ovulation:
 - Oral
 - Intravaginal
 - Transdermal
- Progestogen-only hormonal contraception associated with inhibition of ovulation:
 - Oral
 - Injectable
 - Implantable
- Intrauterine Device (IUD)
- Intrauterine hormone-releasing system (IUS)
- Bilateral tubal occlusion
- Vasectomized partner
- Sexual abstinence

4.4. Prohibited Treatments

Medications intended solely for supportive care are allowed (i.e., antiemetics, analgesics, megestrol acetate for anorexia).

The following concomitant medications are prohibited:

- Concurrent anticancer therapy with agents other than the combination study drug therapy (CMP-001 + pembrolizumab) is not allowed at any time during the study.
- Agents known to have TLR9 antagonist activity are prohibited throughout the study. The current known antagonists are chloroquine, hydroxychloroquine, and quinacrine.
- Systemic pharmacologic doses of corticosteroids > 10 mg/day of prednisone equivalent are not permitted at the time of study enrollment. However, corticosteroid administration is allowed in the following circumstances:
 - In the treatment of subjects with known adrenal insufficiency (see Section 5.1.2.1.1. Consultation with the Medical Monitor is required before enrollment of subjects with adrenal insufficiency)
 - For the management of immune-mediated toxicities
 - For palliation of pain, brain metastases, or other disorders (consultation with the Medical Monitor is required)
- Complementary medications to treat the disease under study (e.g., herbal supplements or traditional Chinese medicines).

4.4.1. Vaccinations

Given the potential for injection site reactions and flu-like symptoms, vaccination with a viral vector or mRNA vaccine should not be performed within 1 week of CMP-001 injection.

4.4.2. Concomitant Procedures

Palliative radiotherapy or palliative surgery may be allowed after Medical Monitor consultation to ascertain whether clinical progression has occurred. If the lesion(s) targeted for palliation are target lesions, then the anatomic site requiring palliation must be assessed for disease status.

4.5. Treatment Discontinuation

Study treatment should continue until 1 of the following occurs:

- Unacceptable adverse event that precludes further study treatment (see Section 5.1.2.5.4 and Section 5.1.3)
- 2 years of study treatment
- PD per RECIST v1.1; continuation of treatment through suspected pseudo-progression is permitted at the Investigator's discretion until confirmed PD per iRECIST (Section 7.2.5)
- Upon request of the Sponsor or regulatory agency
- Clinical disease progression

- If medically necessary in the opinion of the Investigator
- Subject withdraws consent for treatment (note that a subject who withdraws consent for additional study treatment and procedures but not for antitumor response will continue to be followed)
- Subject becomes pregnant or begins breastfeeding
- Subject is lost to follow-up
- Death
- End of Clinical Trial

Subjects who permanently discontinue treatment with pembrolizumab because of immune-mediated AEs must also permanently discontinue treatment with CMP-001.

Subjects will continue study treatment until they reach a reason for treatment or study discontinuation. Clinically stable subjects may continue study treatment beyond RECIST v1.1 progression based upon Investigator judgement of potential benefit. Study treatment may not continue beyond 2 years from initial dose of study treatment.

If a subject achieves and maintains a confirmed CR or iCR by Investigator review, treatment with CMP-001 or the combination of CMP-001 and pembrolizumab may be discontinued at the Investigator's discretion once they meet both of the following criteria:

- Subject has been treated with both study drugs for at least 24 weeks
- Subject has received at least 3 doses of both study drugs beyond the date of the initial CR/iCR

NOTE: 3 doses are required only if medically feasible in the Investigator's opinion – less than 3 doses are acceptable if the Investigator is not medically able to inject.

Subjects who discontinue study treatment should undergo the EOT assessments per [Table 1](#). Subjects who discontinue study treatment for reasons other than disease progression (per RECIST v1.1 or iRECIST by Investigator, or clinical PD per Investigator) should remain on study for PTFU (Section [7.6](#)) and LTSFU (Section [7.7](#)) and receive disease assessments according to the Schedule of Assessments ([Table 1](#)).

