- b. The 30-Day Follow-up is a safety follow-up visit that may be conducted in the study clinic OR via phone. This visit should occur 30 days (+7) after the EOT visit.
- c. PTFU will be conducted every 3 months (\pm 2 weeks) for all subjects who discontinue study treatment but have not met criteria for study discontinuation. These subjects should remain on study and receive disease assessments every 3 months, until discontinuation.
- d. LTSFU will be conducted every 3 months (\pm 4 weeks) after the EOT visit or the last disease assessment date in PTFU and may occur by phone call.
- e. CMP-001 Injection Visits: Weekly Dosing (W1D1 and W2D1): The first dose of CMP-001 may be administered SC or IT, at the discretion of the Investigator; all subsequent doses are planned to be administered IT until no injectable lesions remain. A window of $-2/+5$ days is permitted for CMP-001 dosing on W2D1. Q3W Dosing (W4D1+): A window of ± 3 days is permitted for CMP-001 dosing from W4D1 throughout the trial. When pembrolizumab is permanently discontinued, CMP-001 must also be permanently discontinued. Refer to Section 5.4 for Treatment Compliance.
- f. Pembrolizumab dosing will begin on W1D1 and continue Q3W throughout the study. When CMP-001 injection and pembrolizumab dosing fall on the same day, the CMP-001 injection will be given before pembrolizumab dosing. Refer to Section 5.1.1 for Pembrolizumab Dosing.
- g. A full PE will be conducted at Screening and EOT. If the Screening full PE is performed > 72 hours before the W1D1 visit, then a brief (symptom directed) PE must be performed within 72 hours before the first injection of CMP-001. Brief PEs focused on areas of disease or AEs must be performed at every CMP-001 injection visit, and at any other time as clinically indicated. Height will be obtained at Screening only and weight at all PE assessments.

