Progressive disease (PD) will be assessed by the Investigator according to RECIST v1.1 criteria. Subjects who continue study treatment beyond PD according to RECIST v1.1 will be assessed by the Investigator according to iRECIST.

All scans should be performed at least 2 weeks after the previous CMP-001 IT injection to prevent injection-related pseudoprogression. Imaging should not be delayed for delays in treatment.

Subjects who discontinue study treatment should complete the end of treatment (EOT) visit and 30-day safety follow-up. Subjects who are posttreatment but have not met criteria for study discontinuation should remain on study for posttreatment follow-up (PTFU) and long-term survival follow-up (LTSFU) and receive study evaluations for efficacy according to the Schedule of Assessments ([Table 1](#)).

There is no planned study extension beyond the 2 years of treatment.

Figure 1: CMP-001-007 Study Schema

Abbreviations: 30DFU = 30-Day Follow-up; EOT = End of Treatment; LTSFU = Long-term Survival Follow-up; IT = intratumoral; IV = intravenous; PTFU = Posttreatment Follow-up; Q3W = every 3 weeks; Q12W = every 12 weeks; QW = every week; SC = subcutaneous.

NOTE: The first dose of CMP-001 may be administered by SC or IT injection, per Investigator discretion. All subsequent doses of CMP-001 are planned to be administered IT.

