4.6. Study Withdrawal

Subjects may withdraw from the study at any time and without penalty or loss of future medical care, or any other benefits to which they are otherwise entitled. Subjects will be withdrawn from the study for any of the following reasons:

- Subject withdraws consent for the study
- Subject lost to follow-up
- Death
- End of clinical trial

For subjects who withdraw consent from overall study participation (not only study treatment) will not have the EOT visit, safety follow-up visits, or further evaluations performed.

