4.7. End of Clinical Trial

The End of Clinical Trial (EOT) is defined as the last visit for the last subject on the trial. All data collection will cease in all subjects when End of Clinical Trial is reached.

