7.7. Long-Term Survival Follow-Up

Subjects who discontinue study treatment and PTFU, will be contacted by the site according to the Schedule of Assessments ([Table 1](#)) for LTSFU, which will continue until death, withdrawal of consent, lost to follow-up, or End of Clinical Trial.

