C. Sample Size Status

Given the early termination of site activation and study enrollment since 24Jun2022 per Sponsor's decision, all the analyses will be descriptive and exploratory. The number of subjects included in this study is 24. Subjects who have provided written informed consent once the enrollment goal is reached may be allowed to complete Screening and enter study treatment if they meet all eligibility criteria, at the discretion of the Sponsor or its representatives. As enrollment is terminated, subjects who discontinue the study before receiving the first dose of CMP-001 will not be replaced.

With the enrollment of the last subject on 22Jun2022, the subject status of this study is as follows:

- 39 subjects were screened
- 15 subjects were screen failures
- 24 subjects started the treatment

D. Treatment Randomization

No randomization will be performed in this study.

E. Assessment Schedule

See Protocol Table 1 for the study schedule of assessments.

F. End of Study

Per Sponsor's decision, site activation and study enrollment were terminated officially on 24Jun2022. All subjects previously enrolled in the study may continue receiving up to 2 years of study treatment per the current protocol.

The end of study is defined as the date of the last dose of study treatment for the last ongoing subject, plus 30 days of safety follow-up.

III. Protocol Objectives

Per Sponsor's decision, enrollment was stopped before reaching the sample size planned for the analyses described in the Protocol. All analyses will be exploratory. The performance of the statistical analysis for the protocol objectives and endpoints of the exploratory phase 2 study is contingent on the availability of the data source. Detailed information will be provided in the corresponding sections to follow.

Regeneron Pharmaceuticals Inc. / Protocol: CMP-001-007
IQVIA Biotech (Confidential) Project # SZA56629

A. Primary

- To determine the Investigator-assessed confirmed objective response with CMP-001 in combination with pembrolizumab in subjects with head and neck squamous cell carcinoma (HNSCC).

B. Secondary

- To evaluate the safety and tolerability of CMP-001 administered by intratumoral (IT) injection in combination with pembrolizumab in subjects with HNSCC.
- To evaluate the efficacy of CMP-001 in combination with pembrolizumab in subjects with HNSCC.

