iUPD per iRECIST, continued study treatment with subsequent disease assessments but no confirmed PD (i.e., iCPD not assigned) or Death as of data cutoff date and subject not received new anticancer therapy or received it after the data cutoff date	Censored	Date of the last tumor assessment as of data cutoff date	Alive without Documented iCPD
iUPD per iRECIST, continued study treatment, but started a new anti-cancer therapy before data cutoff date without evidence of iCPD or Death	Censored	Date of the last tumor assessment prior to new anti-cancer therapy	Subsequent Anti-cancer Therapy without Documented iCPD
iCPD per iRECIST or Death after new anticancer therapy and the new anticancer started before data cutoff date	Censored	Date of last disease assessment prior to new anticancer therapy	iCPD or Death after Subsequent Anti-cancer Therapy
iCPD per iRECIST or Death after new anticancer therapy and the new anticancer started after data cutoff date	Censored	Date of last disease assessment on/before data cutoff date	iCPD or Death after Subsequent Anti-cancer Therapy
iUPD per iRECIST, continued study treatment, iCPD or Death immediately following two or more consecutive disease assessments since the last adequate disease assessment	Censored	Date of last adequate tumor assessment prior to the first missed assessment	iCPD or Death after Missing ≥ 2 Consecutive Disease Assessments
Withdraw consent or lost to follow-up before iCPD per iRECIST or death	Censored	Date of last adequate disease assessment	Discontinued from Study without Documented iCPD or Death

Table 1c: Censoring Rules for the OS

Situation	Outcome	Date	Event Description/ Censoring Reason
Death on/before data cutoff date	Event	Date of death	Death
Alive with study completed before data cutoff date	Censored	Study completion date	Alive on or before study completion date
Alive or death after data cutoff date with study continuing on/till after data cutoff date	Censored	Data cutoff date	Alive on or before data cutoff date

Regeneron Pharmaceuticals Inc. / Protocol: CMP-001-007
 IQVIA Biotech (Confidential) Project # SZA56629

Lost to follow-up prior to data cutoff date	Censored	Last known alive date	Discontinued from study
Discontinued study without death and not lost to follow-up on/prior to data cutoff date	Censored	Date of study discontinuation	Discontinued from study

Table 2: Last Contact Date for the Overall Survival

Source Data	Conditions

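### Section 4.5 gives no survival follow-up to subjects who stop for progression, while other sections do; if sites act on it, OS could be censored at progression

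*Protocol*

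**What the plan says.** Protocol 4.5 ends with a rule on follow-up after treatment: "Subjects who discontinue study treatment for reasons other than disease progression (per RECIST v1.1 or iRECIST by Investigator, or clinical PD per Investigator) should remain"; this covers PTFU and LTSFU. One condition governs both phases, and nothing is said about subjects who stop for RECIST, iRECIST or clinical progression.

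The other places read differently:

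- **Protocol 3.1**, in line with the synopsis and SAP II.A: "Subjects who are posttreatment but have not met criteria for study discontinuation should remain on study for posttreatment follow-up (PTFU) and" LTSFU. Progression is not an exclusion.
- **Protocol 4.6**: "Subjects will be withdrawn from the study for any of the following reasons", followed by withdrawal of consent, loss to follow-up, death and end of trial. Progression is not listed.
- **Table 1 note c** (PTFU only): visits are "for all subjects who discontinue study treatment but have not met criteria for study discontinuation", with disease assessments until discontinuation.
- **Table 1 note d**: LTSFU runs from the EOT visit or from the last PTFU assessment, with no progression exclusion.
- **Protocol 7.6**: PTFU disease assessments stop at progression, among other events.
- **Protocol 7.7**: "Subjects who discontinue study treatment and PTFU, will be contacted by the site" until death, withdrawal of consent, loss to follow-up or End of Clinical Trial.
- **SAP Table 1c**: a subject described as "Discontinued study without death and not lost to follow-up on/prior to data cutoff date" is censored for OS at the date of study discontinuation.

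The end of the study is also defined twice. SAP II.F: "The end of study is defined as the date of the last dose of study treatment for the last ongoing subject, plus 30 days", the added days being for safety follow-up. Protocol 4.7: the end of the trial "is defined as the last visit for the last subject on the trial".

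**The concern.** The condition in 4.5 suits scans, because 7.6 ends them at progression anyway. It does not suit survival calls, because OS runs to death. Section 4.5 is where a site would look when a subject stops treatment, and progression is one of the listed reasons for stopping.

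If a progressor is closed out at EOT, there is little to catch the later death. Protocol Table 3 excludes deaths due to progression from SAE reporting, so the LTSFU contact is the main route by which such a death reaches the OS analysis. Table 1c then censors the subject close to progression. Kaplan-Meier assumes that censored subjects carry the same risk of death as those still followed. If risk rises at progression, that assumption fails and OS reads too high. If sites read the text differently, the estimate mixes two follow-up rules.

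**Working it through.** **What the plan sizes.** The documents give no OS calculation to reproduce. The only sizing figure is for ORR (19% v 35%, 80% power, one-sided 0.05): n = [(1.645 × √(0.19 × 0.81) + 0.842 × √(0.35 × 0.65)) / 0.16]² = 42.8, so 43. It reproduces and this point does not touch it.

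**Inputs for the illustration.**
- True median OS 14.9 months: the pembrolizumab monotherapy figure in Protocol 1.1.
- Median PFS 4 months (range 3 to 6) and 15% of PFS events being deaths (range 10% to 25%): assumptions, not in the documents.
- A fraction f of progressors is closed at progression and censored there.

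**Model.** Constant hazards, three states (alive without PD, alive after PD, dead).
- PFS hazard L = ln 2 / 4 = 0.1733 per month.
- Death before PD: h1 = 0.15 × 0.1733 = 0.0260. Progression: k = 0.85 × 0.1733 = 0.1473.
- P0(t) = exp(-L t); P1(t) = k [exp(-h2 t) - exp(-L t)] / (L - h2); S(t) = P0(t) + P1(t).
- Death after PD, h2, is solved from S(14.9) = 0.5, giving h2 = 0.062. True S(12) = 0.588.
- With a fraction f dropped, Kaplan-Meier estimates the survival curve with hazard [h1 P0 + h2 (1 - f) P1] / [P0 + (1 - f) P1]. At f = 1 this is h1 alone, so S(12) = exp(-12 × 0.0260) = 0.732 and the median is ln 2 / 0.0260 = 26.7 months.

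| Progressors dropped | 12-month OS reads | Bias (true 58.8%) |
|---|---|---|
| 25% | 60.3% | +1.5 points |
| 50% | 62.5% | +3.7 points |
| 100% | 73.2% | +14.4 points |

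**Sensitivity.** Over PFS medians of 3 to 6 months and 10% to 15% deaths, the bias is +0.7 to +3.6 points with 25% dropped and +8 to +27 with all dropped. With 25% of PFS events being deaths, full dropout gives about -6 to +12. The sign follows h2 against h1: at PFS 3 months and 25% deaths, h1 = 0.058 exceeds h2 = 0.041 and the bias is negative.

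**Second check by simulation.** This used median PFS of 2, 3 or 5 months, 10% or 20% deaths, true median OS of 10.7 or 14.9 months, progressors dropped 30 days after PD, and 24 months of follow-up. With everyone followed, about 16 to 21 of 24 subjects die on study; with every progressor dropped, about 3 to 7 deaths are seen. Under full dropout the OS median is too high in 9 of 12 scenarios, unbiased in 1 and too low in 2. With 25% dropped it moves by -0.3 to +0.8 months.

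**Scale.** The binomial standard error of 12-month OS in 24 subjects is √(0.588 × 0.412 / 24) = 0.10, or 10 points, before any censoring.

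**The case against.** The strongest reply is that 4.5 is one stray sentence. It never says that only non-progressors are followed, and it does not say that progressors leave the study. Study exit is governed by 4.6, which omits progression, and SAP Table 2 takes last-alive dates from a long-term follow-up eCRF. A site closing a progressor at EOT would be acting against 4.6 and 7.7. This stands: exclusion is the implication of 4.5, not its text, and any harm depends on sites acting on it.

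Three stronger readings are tempting, and the documents do not support them.

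- **OS will be overstated by about 14 points.** That needs every progressor at every site to be dropped, and it rests on assumed PFS and death-share values. Partial adoption gives a few points at most, and the direction is not assured.
- **All data collection stops at the SAP II.F date.** The rule that collection ceases belongs to 4.7 and to its own end point, the last subject's last visit. II.F does not say that collection stops, and SAP I.B states that the SAP need not match the protocol after enrolment closed early. What remains is that two definitions differ.
- **The 18-month rates are compromised.** SAP VIII.C lists 18 months only as an example. The last subject enrolled on 22 June 2022, so 18 months (548 days) of OS falls about 22 December 2023. DOR starts at response, with the first scheduled scan at Week 10 (day 63, or up to 7 days earlier), so its 18 months fall in mid to late February 2024 at the earliest. Treatment may run for two years, so the II.F date could come after both. Fewer subjects at risk would cost precision; it is not the bias described here.

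**Conclusion.** The contradiction is real and should be corrected. Section 4.5 ties survival follow-up to stopping for reasons other than progression; the rest of the protocol and SAP II.A do not. A site that follows 4.5 could create informative censoring of OS with little chance of recovering the deaths elsewhere.

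The consequence is conditional. It requires sites to act on 4.5, and it overstates OS only if mortality is higher after progression than before, for which the documents give no figure. Under the stated assumptions a quarter of progressors dropped costs about 1.5 points of 12-month OS, well inside the 10-point standard error; complete adoption costs about 14.

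OS is a secondary endpoint, and SAP II.C makes all analyses descriptive and exploratory in 24 subjects. The primary ORR is unaffected.

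**What to change.** 1. **Split the 4.5 sentence.** Subjects who stop for reasons other than progression enter PTFU for disease assessments, in line with 7.6. All subjects who stop study treatment for any reason, including RECIST, iRECIST or clinical progression, enter LTSFU until death, withdrawal of consent, loss to follow-up or End of Clinical Trial, as in 7.7.
2. **Align Table 1 note c with 7.6**, so that both give the same stopping events for PTFU scans.
3. **Separately, reconcile SAP II.F with Protocol 4.7**, so that survival and PTFU data collected after the last dose are not left out of the analysis.

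The cost is wording in three places and a note to sites. The 3-monthly contacts are already in Table 1 and may be made by phone. Survival calls would continue for some subjects after the last dose, as 7.7 already commits. Sites should also check whether any progressor has already been closed out, because those deaths may be harder to recover later.
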